4.2.2 Number of Sites

Approximately 1 to 3 investigative sites in United States will be included in the study. Sites that do not enroll subjects within 1 month of site initiation may be closed.

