6.2 Dose Modification

6.2.1 Dose-cohort Study Escalation/De-escalation and Stopping Rules

Dose Level Determination

A recommendation to escalate to a higher dose cohort will only occur when the previous dose regimen(s) have been found to be reasonably well tolerated based on available study data through study day 15 for a minimum of 7 out of 8 dosed subjects (cohorts 1 to 6 and cohort 11) or through study day 36 for 6 of 8 dosed subjects (cohorts 7 to 10) and upon unanimous agreement of the DLRT members. Available data from previous cohorts will also be considered. Dose level recommendations will be made on a treatment cohort basis (not on an individual basis). After receiving the DLRT recommendation, Amgen will render a final decision and will issue a written notification of the dose change decision to investigators. **The DLRT will not make a dose level recommendation after reviewing the safety and tolerability data through study day 36 for subjects in cohorts 12 to 13 as these are terminal cohorts.** Further information on DLRMs is provided in Appendix 3 (Section 11.3).

Dose Cohort Stopping Rules

The DLRT will recommend stopping or modifying dosing if suspected adverse drug reactions, changes in vital signs, ECG, or clinical laboratory results are observed and these changes pose a significant health risk. In addition, dosing will be stopped or modified if any of the stopping rules shown in [Table 11](#) are met. The Amgen medical monitor may suspend dosing and convene a DLRM at any time based on emerging safety data.

Dosing will be stopped or modified as shown in [Table 11](#).

Table 11. Dose Cohort Stopping Rules

Scenario	Action

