Any occurrence of an Amgen Standard Grading Scale moderate adverse event of similar type in 2 or more subjects in the same cohort.	
Stop dosing and convene DLRM (if event occurs outside the regularly scheduled DLRM).
 
Review adverse event and all relevant safety data for evidence of relationship to treatment and clinical or medical significance.
 
Consider unblinding, as appropriate.^a
 
Based on the DLRM vote, 1 of the following recommendations may be made:
 
• stop enrollment of the cohort (if applicable)• resume enrollment of the cohort as planned• expand the cohort at the same dose• continue enrollment of the study at a lower dose• upon a unanimous vote escalate to an intermediate dose (a dose lower than the next planned dose)• upon a unanimous vote escalate to the next planned dose
Any occurrence of an Amgen Standard Grading Scale severe adverse event.	
Stop dosing additional subjects in the cohort and convene DLRM (if the event occurs outside the regularly scheduled DLRM).
 
Review adverse event and all relevant safety data for evidence of relationship to treatment and clinical or medical significance.
 
Consider unblinding to determine relatedness to investigational product.^a
 
If the adverse event is determined by a majority vote of the DLRT to be related to study drug and clinically or medically significant, recommend that no further doses should be administered at this dose and no dose escalation should proceed. Recommend that enrollment of the study continue at a lower dose or a lower dose cohort may be added to the study.
 
Otherwise, based on the majority vote of the DLRT, 1 of the following recommendations may be made:
 
• resume enrollment of the cohort as planned• expand the cohort at the same dose• continue enrollment of the study at a lower dose or add a lower dose cohort to the study.

DLRM = dose level review meeting; DLRT = dose level review team

^a A subject's treatment assignment should only be unblinded when knowledge of the treatment is essential for the further management of the subject or may impact the safety of subjects currently enrolled or of subjects in subsequent cohorts.

Clinically or medically significant serious adverse events and suspected adverse drug reactions considered to be related to study procedures will be followed until resolved or considered stable.

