11.3 Appendix 3. Study Governance Considerations

Dose Level Review Meetings (DLRM)

A DLRM is conducted to review and interpret safety data for the purposes of making recommendations about dose-level escalation (either to the next planned dose or to an intermediate dose), dose level de-escalation, cohort continuation, or cohort expansion; making recommendations about non-dose escalation cohorts (eg, expanded, highest dose and/or final cohort); and evaluating safety signals for purposes of applying Dose Cohort Stopping Rules. The required Dose Level Review Team (DLRT) members are the medical monitor, Global Safety Officer (GSO), and Site Investigators. The DLRT will include actively screening and enrolling Site Investigators. The medical monitor, GSO, and Site Investigators are the only voting DLRT members. The following nonvoting Amgen representatives may also be part of the DLRT: clinical study manager, biostatistician, or pharmacokinetics scientist.

The medical monitor must be in attendance and cannot be represented by a voting designee or delegate. Voting designees can be identified as appropriate by the GSO or site investigator(s). A site investigator may identify a delegate (eg, sub-investigator) who is listed in the Delegation of Authority. If a site investigator does this, the site investigator must provide written agreement with the designee or delegate's vote.

For a DLRM to occur, the medical monitor must attend, and the GSO or delegate must attend. In addition, a quorum of Site Investigators must be present. A quorum is defined as more than 50% of the participating investigators or their qualified designees. The DLRM will be rescheduled if these requirements are not met.

All available study data, including demographics, investigational product administration, medical history, concomitant medications, adverse events, electrocardiogram (ECG), vital signs, and laboratory results will be reviewed. Data to be reviewed will be unqueried.

Data will be reviewed blinded (ie, treatment assignment will not be revealed) unless unblinding is deemed necessary for the review team to make dosing recommendations. If deemed necessary, unblinding will be performed to assist dose change recommendations, in accordance with Amgen standard procedures.

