Dose Level Review Meeting voting will occur as follows: there will be a total of 3 votes, 1 for the medical monitor, 1 for the GSO or delegate, and 1 for all of the Site Investigators or delegates combined. Regardless of how many Site Investigators there

are, all of the Site Investigators combined will have a total of 1 vote decided by a majority of the investigators (defined as greater than or equal to 50%).

Dose Level Review Meeting recommendations to escalate to the next planned cohort, or to an intermediate cohort, must be by unanimous vote. If the voting members of the DLRT are not able to reach a unanimous recommendation on whether to escalate to the next planned cohort or to an intermediate cohort, then this should be reflected in the DLRM Memo. Other recommendations, such as expanding a cohort or lowering a dose will be made by a majority vote.

Regulatory and Ethical Considerations

This study will be conducted in accordance with the protocol and with:

- Consensus ethical principles derived from international guidelines including the Declaration of Helsinki and Council for International Organizations of Medical Sciences International Ethical Guidelines
- Applicable International Council for Harmonisation (ICH) Good Clinical Practice (GCP) Guidelines
- Applicable ICH laws and regulations

The protocol, protocol amendments, informed consent form, investigator's brochure, and other relevant documents (eg, subject recruitment advertisements) must be submitted to an Institutional Review Board (IRB)/Independent Ethics Committee (IEC) by the investigator and reviewed and approved by the IRB/IEC. A copy of the written approval of the protocol and informed consent form must be received by Amgen before recruitment of subjects into the study and shipment of Amgen investigational product.

Amgen may amend the protocol at any time. The investigator must submit and, where necessary, obtain approval from the IRB/IEC for all subsequent protocol amendments and changes to the informed consent document. The investigator must send a copy of the approval letter from the IRB/IEC and amended protocol Investigator's Signature page to Amgen prior to implementation of the protocol amendment at their site.

The investigator will be responsible for the following:

- Providing written summaries of the status of the study to the IRB/IEC annually or more frequently in accordance with the requirements, policies, and procedures established by the IRB/IEC

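### The dose level review counts 50% of the investigators as a majority, so a 1-1 split can be recorded as part of a unanimous escalation

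*Protocol*

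**What the plan says.** Protocol 11.3 (Appendix 3, Dose Level Review Meetings) makes the medical monitor, the GSO and the site investigators the only voting members of the dose level review team (DLRT). On counting, it says "there will be a total of 3 votes, 1 for the medical monitor, 1 for the GSO or delegate", with the third vote held by all site investigators combined. That third vote is "1 vote decided by a majority of the investigators (defined as greater than or equal to 50" (the figure is a percentage).

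Two decision rules use these three votes. For escalation: "Dose Level Review Meeting recommendations to escalate to the next planned cohort, or to an intermediate cohort, must be by unanimous vote". For everything else: "Other recommendations, such as expanding a cohort or lowering a dose will be made by a majority vote". Table 11 in Section 6.2.1 applies the second rule to severe adverse events, with one course of action "If the adverse event is determined by a majority vote of the DLRT to be related to study drug and clinically or medically significant" and a different set of options otherwise.

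On attendance, the same appendix says: "A quorum is defined as more than 50% of the participating investigators or their qualified designees". Section 4.2.2 sets the scale: "Approximately 1 to 3 investigative sites in United States will be included in the study".

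Section 6.2.1 permits escalation only "upon unanimous agreement of the DLRT members". The synopsis (Section 1.1, Dose Level Review Meetings) and SAP 3.1 repeat that condition.

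**The concern.** A majority normally means more than half. If exactly half is enough, an evenly divided group satisfies the rule in both directions, and the recorded result can depend on which way the question was put. With one to three sites, two voting investigators is an ordinary case.

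What is at stake is the meaning of unanimity, the extra protection the protocol attaches to going up in dose in a first-in-human trial. Under Appendix 3 a team can be recorded as unanimous although one of its two investigators voted against. Section 6.2.1, read literally, would not allow that escalation, because site investigators are voting members. The two texts have to be reconciled. The appendix also does not say whether the percentage is taken over the investigators who vote or over all participating investigators, and it has no tie rule.

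**Working it through.** The plan gives no figure to reproduce here; the check is an enumeration of the voting rule.

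**Inputs.** Threshold of at least 50%, three votes in total, unanimity for escalation and majority otherwise, quorum above 50% (all Appendix 3); majority vote on relatedness (Table 11); about 1 to 3 sites (Section 4.2.2). Assumed: one investigator vote per site and no abstentions.

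**Step 1: when can the investigators tie?**

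| Sites | Voting | Even split possible? | Share on each side |
|---|---|---|---|
| 1 | 1 | No | 100% or 0% |
| 2 | 2 (one of two is 50%, which fails the quorum, so both must attend) | Yes, 1-1 | 1/2 = 50% for, 50% against |
| 3 | 2 (2/3 = 67%, quorum met), denominator those present | Yes, 1-1 | 1/2 = 50% for, 50% against |
| 3 | 2, denominator all three | 1-1, but neither side carries | 1/3 = 33% for, 33% against |
| 3 | 3 | No | 67% against 33%, or 100% against 0% |

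So the threshold gives an ambiguous result only when exactly two investigator votes are counted.

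**Step 2: combine a 1-1 tie with the other two votes.**

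| Medical monitor and GSO | At least 50% (as written) | More than 50% |
|---|---|---|
| Both for | 1 + 1 + 1 = 3 of 3: unanimous | 1 + 1 + 0 = 2 of 3: majority, not unanimous |
| Split | For: 1 + 1 = 2 of 3. Against: 1 + 1 = 2 of 3. Both can carry | 1 of 3 each way: neither carries |
| Both against | Against carries | Against carries |

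The first row is the escalation problem. The second is the only case in which the threshold affects a Table 11 relatedness ruling. If the medical monitor and the GSO agree, they already hold 2 of 3 votes, and the ruling stands under either threshold even if every investigator is opposed.

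**Step 3: how often could the two thresholds differ?** Suppose two investigators each oppose independently with probability q. Neither the value of q nor the independence comes from the documents.

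- At least 50%: the vote carries unless both oppose, so 1 - q².
- More than 50%: both must be in favour, so (1 - q)².
- Difference: 1 - q² - (1 - q)² = 2q(1 - q).

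| q | At least 50% | More than 50% | Difference |
|---|---|---|---|
| 0.1 | 99% | 81% | 18 points |
| 0.3 | 91% | 49% | 42 points |
| 0.5 | 75% | 25% | 50 points |

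These figures concern the investigators' combined vote alone. An escalation also needs the medical monitor and the GSO.

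**The case against.** **Escalation is mostly over.** Section 4.3 reports that all single-dose cohorts are complete, Section 2.2.2.4 reports 39 subjects already enrolled in the multiple-dose part, and Section 6.2.1 says cohorts 12 and 13 receive no dose level recommendation. The team only recommends and the sponsor decides. After a severe event, dosing of further subjects in the cohort stops before any vote, and the medical monitor may suspend dosing at any time. All of this stands and limits the reach. It does not remove the point: Sections 4.2 and 9.2 still allow cohorts to be expanded, repeated or added, and Table 11 states no exemption for Part C.

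**A tie need not be a contradiction.** If the 50% threshold applies only to the motion as put, a 1-1 split has one result: the motion passes. That is a possible reading, and the text does not choose between the two. It does not help escalation, because on that reading too a motion to escalate passes with half the investigators opposed.

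**A reader might infer that the wording generally lets a severe event be ruled related, or unrelated, over the objection of half the investigators.** The documents do not support blaming the threshold for that. When the medical monitor and the GSO agree, the three-vote structure gives that result whatever the threshold. Nor do the documents show that any past meeting was tied, or how many investigators vote now.

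**A strict majority does not settle everything.** This is correct. If the medical monitor and the GSO split and the investigators tie, a strict threshold leaves both rulings at 1 of 3, and the alternative branch of Table 11 needs a majority too. A tie rule is needed as well.

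**The probabilities are illustrative.** Also correct. Investigators who review the same data together are unlikely to vote independently. The logical gap does not depend on q.

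**Conclusion.** The voting rule is wrong as written, with narrow reach. When exactly two investigator votes are counted (two sites, or two of three present if those present are the denominator), Appendix 3 lets an escalation be recorded as unanimous with one of the two investigators opposed. That conflicts with Section 6.2.1, the synopsis and SAP 3.1, and it is looser than the appendix's own quorum threshold. For a Table 11 relatedness vote the wording is decisive only when the medical monitor and the GSO also disagree.

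The difference of 18 to 50 points for q between 0.1 and 0.5 shows that the choice of threshold is not trivial when two investigators vote. It rests on assumed values of q and on independence, and is not an estimate of what happened in this trial. The finding on the rule itself needs neither assumption. It concerns decision governance; no analysis in the SAP depends on it.

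**What to change.** Amend Appendix 3 and align the other sections:

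1. Define the investigator majority as more than 50%, and state whether the denominator is the investigators voting or all participating investigators.
2. State that a tied investigator vote does not count as a vote for escalation and is recorded in the review meeting memo, which Appendix 3 already uses to record a failure to reach unanimity.
3. Reconcile the single combined investigator vote with the requirement in the synopsis, Section 6.2.1 and SAP 3.1 that the members agree unanimously, by saying whether unanimity means three of three votes or every voting member.
4. Have the sponsor state how a tie is resolved for majority votes under Table 11. The first change alone leaves a deadlock when the medical monitor and the GSO split.

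The cost is a short governance amendment. It changes no dose level, data collection or analysis. The downside is that a tie may need further discussion or a reconvened meeting.

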1. SITE INFORMATION							
Site Number	Investigator			Country			
Reporter		Phone Number ()			Fax Number ()		
2. SUBJECT INFORMATION							
Subject ID Number	Age at event onset			Sex	Race	If applicable, provide End of Study date	
				 F  M			
If this is a follow-up to an event reported in the EDC system (eg, Rave), provide the adverse event term: _____ and start date: Day _____ Month _____ Year _____							
3. SERIOUS ADVERSE EVENT							
Provide the date the Investigator became aware of this information: Day Month Year							
Serious Adverse Event diagnosis or syndrome If diagnosis is unknown, enter signs / symptoms and provide diagnosis, when known, in a follow-up report List one event per line. If event is fatal, enter the cause of death. Entry of "death" is not acceptable, as this is an outcome.		Date Started	Date Ended	Check only if event occurred before first dose of IP	Is serious, enter Serious Criteria code (see codes below)	Relationship	Outcome of Event
		Day Month Year	Day Month Year		AMG 133 No ^v Yes ^v	Is there a reasonable possibility that the Event may have been caused by IP or an Amgen device used to administer the IP?	Resolved Not resolved Fatal Unknown
				 Yes  No			
				 Yes  No			
				 Yes  No			
Serious Criteria: 01 Fatal 02 Immediately life-threatening		03 Required/prolonged hospitalization 04 Persistent or significant disability /incapacity			05 Congenital anomaly / birth defect 06 Other medically important serious event		
4. Was subject hospitalized or was a hospitalization prolonged due to this event?  No  Yes If yes, please complete all of Section 4							
Date Admitted Day Month Year				Date Discharged Day Month Year			
5. Was IP/drug under study administered/taken prior to this event?  No  Yes If yes, please complete all of Section 5							
IP/Amgen Device: AMG 133		Date of Initial Dose	Date of Dose	Dose	Route	Frequency	Action Taken with Product
		Day Month Year	Day Month Year				01 Still being Administered 02 Permanently discontinued 03 Withheld
							Lot # _____  Unknown Serial # _____  Unavailable / Unknown

A Study # 20180048 AMG 133	Electronic Serious Adverse Event Contingency Report Form For Restricted Use										
		Site Number		Subject ID Number							
6. CONCOMITANT MEDICATIONS (eg, chemotherapy) Any Medications?  No  Yes If yes, please complete:											
Medication Name(s)		Start Date Day Month Year	Stop Date Day Month Year	Co-suspect No✓  Yes✓ 	Continuing No✓  Yes✓ 	Dose	Route	Freq.	Treatment Med No✓  Yes✓ 		
7. RELEVANT MEDICAL HISTORY (include dates, allergies and any relevant prior therapy)											
8. RELEVANT LABORATORY VALUES (include baseline values) Any Relevant Laboratory values?  No  Yes If yes, please complete:											
Date Day Month Year	Test										
	Unit										
9. OTHER RELEVANT TESTS (diagnostics and procedures) Any Other Relevant tests?  No  Yes If yes, please complete:											
Date Day Month Year	Additional Tests				Results				Units		

11.5 Appendix 5. Contraceptive Guidance and Collection of Pregnancy and Lactation Information

Study-specific contraception requirements for male and female of childbearing potential are outlined in Section 5.2.

Male and female subjects of childbearing potential must receive pregnancy prevention counseling and be advised of the risk to the fetus if they become pregnant or father a child during treatment and for 5 months after the last dose of protocol-required therapies.

Definition of Females of Childbearing Potential

A female is considered fertile following menarche and until becoming postmenopausal unless permanently sterile. Permanent sterilization methods include hysterectomy, bilateral salpingectomy, and bilateral oophorectomy.

Females in the following categories are not considered female of childbearing potential:

- Premenopausal female with 1 of the following:
 - Documented hysterectomy;
 - Documented bilateral salpingectomy; or
 - Documented bilateral oophorectomy.

Note: Site personnel documentation from the following sources is acceptable:

- 1) review of subject's medical records; 2) subject's medical examination; or
- 3) subject's medical history interview.

- Premenarchal female
- Postmenopausal female
 - A postmenopausal state is defined as no menses for 12 months without an alternative medical cause. A high follicle stimulating hormone (FSH) level in the postmenopausal range may be used to confirm a postmenopausal state in women not using hormonal contraception or hormonal replacement therapy (HRT). However, in the absence of 12 months of amenorrhea, a single FSH measurement is insufficient.
 - Females on HRT and whose menopausal status is in doubt will be required to use 1 of the non-hormonal highly effective contraception methods if they wish to continue their HRT during the study. Otherwise, they must discontinue HRT to allow confirmation of postmenopausal status before study enrollment

Contraception Methods for Male Subjects

- Sexual abstinence (defined as refraining from heterosexual intercourse during the entire period of risk associated with protocol-required therapies; the reliability of sexual abstinence must be evaluated in relation to the duration of the trial and the preferred and usual lifestyle of the subject)
- Use a condom during treatment and for an additional 5 months after the last dose of protocol-required therapies

The female partner should consider using an acceptable method of effective contraception such as: hormonal, intrauterine device, intrauterine hormonal-releasing system, female barrier method (diaphragm, cap, sponge [a female condom is not an option because there is a risk of tearing when both partners use a condom]).

Note: If the male's sole female partner is of non-childbearing potential or has had a bilateral tubal ligation/occlusion, he is not required to use additional forms of contraception during the study.

Unacceptable Methods of Birth Control for Male and Female Subjects

Birth control methods that are considered unacceptable in clinical trials include:

- Periodic abstinence (calendar, symptothermal, postovulation methods)
- Withdrawal (coitus interruptus)
- Spermicides only
- Lactational amenorrhea method

Collection of Pregnancy Information

Female Subjects Who Become Pregnant

- Investigator will collect pregnancy information on any female subject who becomes pregnant while taking protocol-required therapies through 5 months after the last dose of investigational product.
- Information will be recorded on the Pregnancy Notification Form (see [Figure 11-2](#)). The form must be submitted to Amgen Global Patient Safety within 24 hours of learning of a subject's pregnancy. (Note: Sites are not required to provide any information on the Pregnancy Notification Form that violates the country or regions local privacy laws).
- After obtaining the female subject's signed authorization for release of pregnancy and infant health information, the investigator will collect pregnancy and infant health information and complete the pregnancy questionnaire for any female subject who becomes pregnant while taking protocol-required therapies through 5 months after the last dose of investigational product. This information will be forwarded to Amgen Global Patient Safety. Generally, infant follow-up will be conducted up to 12 months after the birth of the child (if applicable).
- Any termination of pregnancy will be reported to Amgen Global Patient Safety, regardless of fetal status (presence or absence of anomalies) or indication for procedure.

- While pregnancy itself is not considered to be an adverse event or serious adverse event, any pregnancy complication or report of a congenital anomaly or developmental delay, fetal death, or suspected adverse reactions in the neonate will be reported as an adverse event or serious adverse event. Note that an elective termination with no information on a fetal congenital malformation or maternal complication is generally not considered an adverse event, but still must be reported to Amgen as a pregnancy exposure case.
- If the outcome of the pregnancy meets a criterion for immediate classification as a serious adverse event (eg, female subject experiences a spontaneous abortion, stillbirth, or neonatal death or there is a fetal or neonatal congenital anomaly) the investigator will report the event as a serious adverse event.
- Any serious adverse event occurring as a result of a poststudy pregnancy which is considered reasonably related to the study treatment by the investigator, will be reported to Amgen Global Patient Safety as described in Section 11.4. While the investigator is not obligated to actively seek this information in former study subjects, he or she may learn of a serious adverse event through spontaneous reporting.
- Any female subject who becomes pregnant while participating will discontinue study treatment (see Section 7.1 for details).

Male Subjects With Partners Who Become Pregnant

- In the event a male subject fathers a child during treatment, and for an additional 5 months after discontinuing protocol-required therapies, the information will be recorded on the Pregnancy Notification Form. The form (see Figure 11-2) must be submitted to Amgen Global Patient Safety within 24 hours of the site's awareness of the pregnancy. (Note: Sites are not required to provide any information on the Pregnancy Notification Form that violates the country or regions local privacy laws).
- The investigator will attempt to obtain a signed authorization for release of pregnancy and infant health information directly from the pregnant female partner to obtain additional pregnancy information.
- After obtaining the female partner's signed authorization for release of pregnancy and infant health information, the investigator will collect pregnancy outcome and infant health information on the pregnant partner and her baby and complete the pregnancy questionnaires. This information will be forwarded to Amgen Global Patient Safety.
- Generally, infant follow-up will be conducted up to 12 months after the birth of the child (if applicable).
- Any termination of the pregnancy will be reported to Amgen Global Patient Safety regardless of fetal status (presence or absence of anomalies) or indication for procedure.

Collection of Lactation Information

- Investigator will collect lactation information on any female subject who breastfeeds while taking protocol-required therapies through 5 months after the last dose of investigational product.

- Information will be recorded on the Lactation Notification Form (see below) and submitted to Amgen Global Patient Safety within 24 hours of the investigator's knowledge of event.
- Study treatment will be discontinued if female subject breastfeeds during the study as described in exclusion criterion 226.
- With the female subjects signed authorization for release of mother and infant health information, the investigator will collect mother and infant health information and complete the lactation questionnaire on any female subject who breastfeeds while taking protocol-required therapies through 5 months after discontinuing protocol-required therapies.

Figure 11-2. Pregnancy and Lactation Notification Forms

Amgen Proprietary - Confidential

AMGEN® Pregnancy Notification Form

Report to Amgen at: USTO [contact], Non-US [contact] or email (worldwide): [contact]

1. Case Administrative Information

Protocol/Study Number: 20180048

Study Design: Interventional Observational (If Observational: Prospective Retrospective)

2. Contact Information

Investigator Name _____ Site # _____

Phone (____) _____ Fax (____) _____ Email _____

Institution _____

Address _____

3. Subject Information

Subject ID # _____ Subject Gender: Female Male Subject age (at onset): _____ (in years)

4. Amgen Product Exposure

Amgen Product	Dose at time of conception	Frequency	Route	Start Date
				mm____/dd____/yyyy____

Was the Amgen product (or study drug) discontinued? Yes No

If yes, provide product (or study drug) stop date: mm ____/dd ____/yyyy ____

Did the subject withdraw from the study? Yes No

5. Pregnancy Information

Pregnant female's last menstrual period (LMP) mm____/dd____/yyyy____ Unknown N/A

Estimated date of delivery mm____/dd____/yyyy____
If N/A, date of termination (actual or planned) mm____/dd____/yyyy____

Has the pregnant female already delivered? Yes No Unknown N/A

If yes, provide date of delivery: mm____/dd____/yyyy____

Was the infant healthy? Yes No Unknown N/A

If any Adverse Event was experienced by the infant, provide brief details:

Form Completed by:

Print Name: _____ Title: _____

Signature: _____ Date: _____

Amgen Proprietary - Confidential

AMGEN® Lactation Notification Form

Report to Amgen at: USTO [contact], Non-US [contact] or email (worldwide): [contact]

1. Case Administrative Information

Protocol/Study Number: 20180048

Study Design: Interventional Observational (If Observational: Prospective Retrospective)

2. Contact Information

Investigator Name _____ Site # _____

Phone (____) _____ Fax (____) _____ Email _____

Institution _____

Address _____

3. Subject Information

Subject ID # _____ Subject age (at onset): _____ (in years)

4. Amgen Product Exposure

Amgen Product	Dose at time of breast feeding	Frequency	Route	Start Date
				mm ____/dd ____/yyyy ____

Was the Amgen product (or study drug) discontinued? Yes No

If yes, provide product (or study drug) stop date: mm ____/dd ____/yyyy ____

Did the subject withdraw from the study? Yes No

5. Breast Feeding Information

Did the mother breastfeed or provide the infant with pumped breast milk while actively taking an Amgen product? Yes No

If No, provide stop date: mm ____/dd ____/yyyy ____

Infant date of birth: mm ____/dd ____/yyyy ____

Infant gender: Female Male

Is the infant healthy? Yes No Unknown N/A

If any Adverse Event was experienced by the mother or the infant, provide brief details: _____

Form Completed by:

Print Name: _____ Title: _____

Signature: _____ Date: _____

